6.5.3. Clinical Laboratory Evaluations

The urine pregnancy test performed at the final visit for SD-005 will be utilized for entry (Visit 1) into SD-006 only if the visits occur on the same day, otherwise, urine pregnancy test will be performed at Visit 1. Urine pregnancy tests for female patients of child bearing potential (sensitivity at least 25 mIU/ml) will also be performed at Visit 3 through Visit 18.

6.5.4. Physical Examination including Height/Length, Weight and Temperature

The physical examination performed at the final visit for SD-005 will be utilized as the baseline assessment for SD-006 unless Visit 1 is ≥ 14 days after the final SD-005 visit, in which case a physical examination will be repeated. An additional physical examination will be done by a physician at Visit 18. The following sites will be examined: head, eyes, ears, nose, throat, neck, chest, lungs, heart, abdomen, skin, and lymph nodes; and the following systems will be assessed: musculoskeletal and neurological. Weight, height/length, and temperature will be recorded.

7. STATISTICAL METHODS

7.1. General Methodology

The final analysis after the study completion will be preceded by at least one interim analysis.

Data will be summarized by treatment groups (based on 005 study treatment: Placebo → SD-101-6.0 and SD-101-6.0 → SD-101-6.0) and overall (where appropriate). Summary and analysis tables will include number of patients (n), mean, standard deviation, median, minimum, and maximum values for all continuous variables. When appropriate, two-sided 95% confidence intervals may be used.

In summary tables of categorical variables counts and percentages will be presented. The denominator for each percentage will be the number of patients within the population (unless otherwise specified).

All analyses for efficacy will be performed using the Intent-To-Treat (ITT) population, all safety analyses will be performed using the safety population. No comparison between treatment groups will be performed. The comparison to baseline will be done by visit in Placebo → SD-101-6.0 group. All hypothesis testing will be two-sided. P-values less than 0.001 will be reported as <0.001 in summary tables.

All statistical analysis will be performed using SAS[®] v9.2 or higher.

7.2. Adjustments for Covariates

No covariates are planned to be used in the analyses for this study.

7.3. Handling of Dropouts or Missing Data

Dropout patients will not be replaced in this study. Missing data will not be imputed unless specified otherwise in the following section.

7.4. Multi-center Studies and Pooling of Centers

Data will be pooled across all study sites. The justification for pooling is made on the basis of three important factors: 1) all study sites use one common protocol, 2) sites are actively and adequately monitored to ensure protocol compliance, 3) all sites use a common data reporting method and data collection procedures⁽¹⁾.

7.5. Multiple Comparisons/Multiplicity

No multiple comparisons and multiplicity adjustment will be used for this study.

7.6. Examination of Subgroups

Safety summaries will be presented by subgroups of gender, age (28 days to <2 years, 2 years to <12 years, 12 years to ≤ 18 years, >18 years),.

8. STATISTICAL ANALYSIS

8.1. Disposition of Patients

The number and percentage of patients who were enrolled, treated, and completed the study will be summarized. Similar summaries will be provided for those patients who discontinued from the study prematurely. For those patients who discontinue early, the reasons for discontinuing will also be summarized. The disposition of all patients will be listed.

Data on screening failures (patients who signed informed consent but were not entered into the trial) will be collected with a yes or no on the CRF and will be presented in a listing.

8.2. Protocol Deviations

Number and percentage of patients with major protocol deviations will be summarized for the ITT population. A final list of patients who have any major protocol deviations will be documented before interim and final database locks. A listing of patients with major protocol deviations will be provided.

8.3. Analysis Populations

8.3.1. Intent-to-Treat (ITT) Population

The intent-to-treat (ITT) population will be defined as all patients who have rolled over from SD-005.

8.3.2. Safety Population

The safety population is defined as all randomized patients who applied/were administered the study medication at least once.

The Intent-to-Treat (ITT) population will be used for all efficacy analyses. The Safety population will be used for all safety analyses. The Per Protocol (PP) population will be used for supportive analyses of the efficacy endpoints.

If the Safety population and ITT populations are identical, then the efficacy and safety analyses will be performed using the ITT population only.

8.4. Demographic and Other Baseline Characteristics

Descriptive summaries of demographic and baseline characteristics will be presented for the ITT Population.

Continuous variables such as patient age, weight, height, body mass index (BMI), BSAI (for lesion and wound burden), and temperature will be summarized as described previously. Categorical variables such as patient gender, , age group (28 days to <2 years, 2 years to <12 years, 12 years to < 18years, 18 years to < 65 years, 65 years to <85 years, >=85 years), EB type, and baseline target wound size (=0, >0) will be summarized using number of observations and percentages for each category.

Enrollment by country will be summarized.

Medical history, including disease history will be summarized and listed.

8.5. Prior and Concomitant Therapy

The World Health Organization (WHO) Drug Dictionary will be used to classify medications for the purpose of the first interim analysis. The WHO Drug Dictionary version might be updated in the future analyses and if so it will be properly footnoted on all tables and listings. Any medication taken before and continuing after first application of SD-101-6.0 in the study SD-006 is considered a concomitant medication. Any medication given before first application but discontinued prior to first application is considered a prior medication. A medication can be considered both prior and concomitant. Medications missing both start and stop dates, or having a start date prior to the last dose of study drug and missing the stop date, or having a stop date after the start of study drug and missing the start date, will be considered concomitant. Medications will also be considered concomitant if partial start and stop dates are present but it cannot be determined if the medication ended prior to start of study drug.

A summary table will be provided for each of the following in the safety population:

1. Number and percentage of patients who had previous therapies/medications by Anatomical Therapeutic Chemical (ATC) code text and WHO drug name
2. Number and percentage of patients who had concomitant therapies/medications by ATC text and WHO drug name

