13.4. Concomitant Medications

All concomitant medications will be recorded. In addition, concomitant medications will be coded for those patients that experience adverse events.

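### SAP 8.5 has no rule that makes a medication concomitant when it is started on study and has a recorded stop date, so completed on-study courses enter neither medication table

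*SAP*

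**What the plan says.** SAP 8.5 (Prior and Concomitant Therapy) gives two definitions that apply when the dates are known:

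- Concomitant: "Any medication taken before and continuing after first application of SD-101-6.0 in the study SD-006 is considered a concomitant medication".
- Prior: "Any medication given before first application but discontinued prior to first application is considered a prior medication".

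It adds that "A medication can be considered both prior and concomitant".

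The remaining clauses handle incomplete dates. A medication is concomitant if both dates are missing. It is also concomitant when "having a start date prior to the last dose of study drug and missing the stop date" applies, or when "having a stop date after the start of study drug and missing the start date, will be considered concomitant". The last clause covers records where "partial start and stop dates are present but it cannot be determined if the medication ended prior to start of study drug".

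Two tables for the safety population follow, one for prior therapy and one described as "Number and percentage of patients who had concomitant therapies/medications by ATC text and WHO drug name".

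Protocol 10.6 (Concurrent Therapy) lets the investigator give any medication the patient needs during the study and requires it to be entered in the eCRF. The schedule in Protocol 11 checks concomitant use at every visit. Protocol 13.4 states "All concomitant medications will be recorded" and provides for coding in patients who have adverse events.

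**The concern.** Both definitions for dated records require that the patient was already using the medication before first application. A treatment begun during the study and finished during the study has no category. The clauses for incomplete dates do admit on-study starts, but only when a date is missing or unclear, so whether a new treatment is counted depends on whether its stop date was recorded.

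What is at stake is the reading of the safety data. Long-term safety is the primary objective (Protocol 7.1, SAP 3), planned treatment runs to 1440 days, and there is no concurrent control. A short course given for an event, for example an anti-infective or an analgesic, is context that a safety reader looks for. SAP 6.5.2 also plans a medical review of whether adverse events could be related to contamination of the study medication, for which newly started treatments are relevant background.

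**Working it through.** The point concerns a classification rule, so the plan has no figure to reproduce. The check applies the clauses of SAP 8.5, as worded, to typical date patterns.

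**Inputs.** First application F = Day 1, which follows the SAP 6.2.1 count of relative days on study drug. Last application L = Day 1440, the planned duration, used for illustration only. The start and stop days below are made up.

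**Rules as written**, with start s and stop e:

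- Concomitant, dates known: s < F and e > F.
- Prior, dates known: s < F and e < F.
- Concomitant, stop missing: s < L.
- Concomitant, start missing: e > F.
- Concomitant, both missing: always.

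**Added rule under test**, dates known: concomitant if s ≤ L and e ≥ F.

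| Start | Stop | SAP 8.5 as written | With the added rule |
|---|---|---|---|
| Day −50 | Day −10 | prior | prior |
| Day −50 | Day 100 | concomitant | concomitant |
| Day −50 | Day 1 | neither | concomitant |
| Day 1 | Day 30 | neither | concomitant |
| Day 200 | Day 214 | neither | concomitant |
| Day 200 | missing | concomitant | concomitant |
| missing | Day 214 | concomitant | concomitant |
| missing | missing | concomitant | concomitant |
| Day 1450 | Day 1455 | neither | neither |

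**The key rows.** For Day 200 to Day 214, s < F would need 200 < 1, which is false, so both dated definitions fail. No missing-date clause applies because both dates are present. Remove the stop date and the missing-stop clause applies, since 200 < 1440, and the record is counted. Under the added rule the dated record passes: 200 ≤ 1440 and 214 ≥ 1. A course entirely after the last application stays out, because 1450 ≤ 1440 is false.

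**Partial dates.** The partial-date clause applies only when it is unclear whether use ended before study drug. If a partial stop date can only fall after first application, that is not unclear, so on a literal reading this clause does not rescue an on-study course either.

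**Elsewhere in the documents.** Protocol 10.6, 11 and 13.4 secure the collection of the data but do not classify them. SAP 8.5 mentions listings only in connection with dictionary versions and specifies no medication listing that would show the omitted records.

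**The case against.** The best defence is that this is a drafting slip that will do no harm. The missing-stop clause accepts any start up to the last dose, so the authors evidently meant on-study starts to count, and a programmer may include them by convention. The data are collected, and the output is one descriptive table. The evidence about intent stands and is a reason to expect ready agreement to the change. It does not repair the text: someone who programs or validates from SAP 8.5 as worded obtains a different table.

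A reader might also infer several stronger things that the documents do not support.

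- *That the table is only a table of baseline medication, or that every on-study start is lost.* On-study starts without a stop date are counted, as are records with an on-study stop and no start. A blank stop date need not be a poor record either, since a medication still in use has none.
- *That the sentence allowing both categories is a plain contradiction.* No single fully dated record can satisfy both definitions. But the tables count patients by drug, so a patient with one course that ended before first application and another that continues across it can properly appear under that drug in both. The sentence is unclear; it is not proven wrong.
- *That a percentage can be put on the understatement.* The documents give no medication data, and any figure would also need the share of new starts with a recorded stop date.
- *That the definition of prior must change too.* Closing the gap does not require it.

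**Conclusion.** The gap is real on the wording of SAP 8.5. A medication started on or after first SD-006 application with a recorded stop date is neither prior nor concomitant and enters neither summary table, while the same medication without a stop date is counted as concomitant. Read strictly, a medication stopped on the day of first application is also left without a category.

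The consequence is limited but one-sided: completed on-study courses are omitted from a descriptive safety-population table. No endpoint, test, analysis population or sample size depends on it. The number of records or patients affected cannot be derived from the documents. The period over which such courses could accrue will often be shorter than 1440 days, because SAP 5.1 reports that sites were told in June 2018 to stop application.

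The conclusion assumes that the table is programmed from the text as it stands. It should be corrected because the table supports the primary objective and the remedy is cheap.

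**What to change.** Replace the definition of concomitant medication in SAP 8.5 with: any medication, whatever its start date, that starts on or before the last SD-006 application and either stops on or after the first SD-006 application or is ongoing. Keep the existing rules for missing dates. State that a partial stop date that can only fall on or after first application is treated as such.

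The definition of prior medication can stay as it is. If it does, either delete the sentence allowing a medication to be both prior and concomitant, or explain that it refers to a patient with separate courses of the same drug and not to a single record.

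The cost is one replaced definition, the partial-date statement, one clarified or deleted sentence and one derivation line. In the patterns checked, no record already classified changes category. No new data are needed, since the protocol already requires these medications to be recorded. If interim medication tables have been produced, confirm which rule was programmed and rerun them if it was the literal one.

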8.6. Analysis of Efficacy Parameters

8.6.1. Analysis of BSAI

No comparison between treatment groups will be performed. The comparison to baseline will be done by visit in Placebo → SD-101-6.0 group using the paired t-test.

- Change in extent of lesional skin based on BSAI at each visit compared to baseline.

To evaluate post-baseline BSAI of lesional skin, both change from baseline and percentage change from baseline will be explored using descriptive statistics. Change from baseline will be calculated as the post-baseline measurement minus the baseline value. Percentage change from baseline will be calculated as the change from baseline divided by the baseline value times 100.

Graphs of the mean change and mean percentage change from baseline over time will also be presented.

- Change in total wound burden based on BSAI at each visit compared to baseline.

This assessment will be analyzed using the same approach for lesional skin as the total body wound burden to both change from baseline and the percentage change from baseline.

Graphs of the mean change and mean percentage change from baseline over time will also be presented.

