9.3. Secondary Endpoints

The secondary endpoints include the change from baseline in BSA coverage of lesional skin and wound burden; as well as closure of unhealed target wounds from the SD-005 study.

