12. EFFICACY ASSESSMENTS

The body surface coverage (BSA) of lesional skin and wound burden will be measured at each visit via the BSAI as described in Sections 9.3.1 and 9.3.2 to monitor the extent of coverage with extended use of ZORBLISA.

Any target wound not completely healed during the SD-005 study will continue to be monitored for closure at each study visit, as described in Section 9.3.3.

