14.3. Analysis Considerations

In general, results will be summarized using descriptive statistics. Summary statistics to be used include proportion of patients with complete closure of their target lesion at each visit, mean and standard deviation of BSAI compared with baseline at each visit, and incidence rates of specific adverse events.

Additional evaluations may be made to compare responses of patients in this extension study with their responses in SD-005. For those patients randomized to ZORBLISA in SD-005, the use of summary statistics as described in the previous paragraph will provide an understanding of the long term effect of ZORBLISA in these patients. For those patients randomized to the control arm in SD-005, summary statistics will be used to compare their response to ZORBLISA in SD-006 with their response to control in SD-005.

In addition to the evaluations described above for the primary efficacy and safety variables, secondary and exploratory variables will also be evaluated using summary statistics.

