3. STUDY OBJECTIVE

The primary objective is to demonstrate the long-term safety of SD-101-6.0 in patients with Simplex, Recessive Dystrophic, and Junctional non-Herlitz epidermolysis bullosa.

The secondary objectives are to assess the efficacy of SD-101-6.0 in terms of the change in Body Surface Area Index (BSAI) of lesional skin and BSAI of wound burden; as well as assessment of healing of unhealed target wounds in patients rolling over from the SD-005 study.

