5.2. Changes from the Analyses Planned in the Protocol/CIP

Subgroup analysis deleted from efficacy analyses. Safety analysis limited to age subgroups.

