6.4. Efficacy Assessments

6.4.1. Change in Body Surface Area Index (BSAI)

- Change in lesional skin based on BSA estimates at Month 1, 3, 6, 9, 12, 15, 18, 21, 24, 27, 30, 33, 36, 39, 42, 45, and 48 compared to baseline will be measured using the Body Surface Area Index (BSAI), where change is defined as the corresponding month value minus the baseline value.
- The BSAI is a global measure of disease extent with weighting factors. The BSA affected with lesional skin will be calculated at baseline and at each visit to assess the total affected area before and after using the product. The BSAI of lesional skin will be assessed as listed in Section 11.1.
- Change in total body wound coverage based on BSAI estimates at Months 1, 3, 6, 9, 12, 15, 18, 21, 24, 27, 30, 33, 36, 39, 42, 45, and 48 compared to baseline will be measured using the BSAI, where change is defined as the corresponding month value minus the baseline value. The BSAI of wounds will be assessed as listed in Section 11.2. Due to the termination of the study data at later time points will be limited.

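### The SAP keeps target-wound healing as a secondary objective but plans no analysis of it and does not list the omission among its changes from the protocol

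*SAP*

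**What the plan says.** Protocol 9.3 names three secondary endpoints: change in lesional-skin BSA, change in wound burden, "as well as closure of unhealed target wounds from the SD-005 study". Protocol 12 adds: "Any target wound not completely healed during the SD-005 study will continue to be monitored for closure at each study visit". Protocol 14.3 lists among its summary statistics the "proportion of patients with complete closure of their target lesion at each visit".

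SAP section 3 carries the objective over: "as well as assessment of healing of unhealed target wounds in patients rolling over from the SD-005 study". SAP 4.1 describes the wound assessment, and SAP 6.3.1 defines its baseline and excludes only wounds already closed at the end of SD-005.

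The SAP's analysis text does not follow this through. Section 6.4 (efficacy assessments) has one subsection, on change in BSAI. Section 8.6 has one subsection, "8.6.1. Analysis of BSAI". The only target-wound output is a baseline category, area zero or above zero, in SAP 8.4. SAP 5.2, which exists to record departures from the planned analyses, says in full: "Subgroup analysis deleted from efficacy analyses. Safety analysis limited to age subgroups".

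The general rules that would otherwise apply are SAP 7.1 (percentages use the whole population unless stated otherwise) and SAP 7.3 (missing data are not imputed unless stated otherwise). Under protocol 9.3.3 and SAP 4.1, ARANZ measurement ends once closure is documented; a closed wound is then assessed for scarring. Footnote e of SAP Table 1 states that no target-wound data were captured at the Month 48/end-of-study visit.

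**The concern.** A stated objective with no planned analysis cannot be answered from the SAP. A reader who turns to 5.2 for departures from the protocol would conclude that closure is still to be reported.

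The gap also leaves open how closure would be counted if someone added it later. A wound that has closed has no further ARANZ reading, so at each later visit it could count as closed, as missing, or as outside the denominator. The rules would then be chosen after the stop in June 2018, in an open-label study, by people who may have seen the readings.

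**Working it through.** **Step 1. Trace the endpoint through both documents.** There is no stated figure to reproduce, since about 150 patients is a roll-over expectation and not a calculation.

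| Item | Lesional BSAI | Wound BSAI | Target-wound closure |
|---|---|---|---|
| Secondary endpoint, protocol 9.3 | yes | yes | yes |
| Summary planned, protocol 14.3 | yes | yes | yes, by visit |
| Objective kept, SAP 3 | yes | yes | yes |
| Assessment defined, SAP 6.4 | yes | yes | no |
| Analysis planned, SAP 8.6 | yes | yes | no |
| Change declared, SAP 5.2 | not needed | not needed | no |

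Two of three secondary endpoints have an analysis. This step needs no assumption.

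**Step 2. Assumptions for the sizes below.** The documents give no closure, reopening or dropout rates and no count of open wounds, so everything from here is illustration. Let q be the share of open wounds closing per 90 days: 0.20, range 0.10–0.30. Only patients with an open wound at entry are considered. Without reopening or dropout, ever closed at Month 12 = 1 − (1−q)^4 = 1 − 0.80^4 = 0.590 (0.344 at q = 0.10; 0.760 at q = 0.30).

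**Step 3. The existing defaults.** Assume 75 of 150 patients have an open wound (range 50–100).
- Whole-population denominator (7.1): 0.590 × 75/150 = 0.295 (0.197–0.394).
- If post-closure visits are also left as missing (7.3), only closures new since Month 9 count: 0.80^3 − 0.80^4 = 0.102, and 0.102 × 75/150 = 0.051 (0.034–0.068).

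Neither figure describes closure among patients who could close.

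**Step 4. Ever documented closed versus closed at the visit.** Let r be the share of closed wounds reopening per 90 days. Use a two-state model with closing rate λ = −ln(1−q)/90 and reopening rate μ = −ln(1−r)/90. A wound open now is open after t days with probability P(t) = [μ + λ·exp(−(λ+μ)t)]/(λ+μ). Visits are at days 30, 90, 180, 270 and 360. For q = 0.20 and r = 0.10: P(30) = 0.9295, P(60) = 0.8664, P(90) = 0.8098, P(360) = 0.5033.
- Ever documented closed = 1 − 0.9295 × 0.8664 × 0.8098^3 = 0.572.
- Closed at day 360 = 1 − 0.5033 = 0.497.
- Gap: about 8 points.

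With r = 0.05 the pair is 0.582 and 0.542; with r = 0.20 it is 0.553 and 0.416. Over q = 0.10–0.30 and r = 0.05–0.20 the gap is 2 to 17 points.

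**Step 5. Dropout handling.** Let a share d of still-open patients leave after each of the first three 90-day intervals, with no reopening. For q = 0.20 and d = 0.10:
- closures per interval: 0.200 + 0.144 + 0.104 + 0.075 = 0.522 of all initially unhealed;
- Kaplan–Meier: 0.590;
- closed/(closed + still followed) = 0.522/(0.522 + 0.299) = 0.636.

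The spread is 0.636 − 0.522, about 11 points. Over q = 0.10–0.30 and d = 0.05–0.15 it is 4 to 17 points.

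**Step 6. The missing end-of-study reading.** A wound open at its last ARANZ reading g days before the stop may close unseen with probability 1 − (1−q)^(g/90), at most q when g = 90. Multiply by the share still open.

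| q | Stop at Month 12: (1−q)^4 × q | Stop at Month 24: (1−q)^8 × q |
|---|---|---|
| 0.10 | 0.656 × 0.10 = 0.066 | 0.430 × 0.10 = 0.043 |
| 0.20 | 0.410 × 0.20 = 0.082 | 0.168 × 0.20 = 0.034 |
| 0.30 | 0.240 × 0.30 = 0.072 | 0.058 × 0.30 = 0.017 |

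Ever-closure is understated by at most about 8 points for a stop at Month 12 and about 4 points at Month 24.

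**The case against.** **It is a minor reporting gap.** SD-006 is an open-label, single-arm safety extension with a safety primary endpoint, no between-group comparison, a sample size set by roll-over and an early stop. Closure was only ever to be described. This stands, and it limits the severity: a reader might infer a critical defect in the trial, but nothing in the safety or BSAI analyses depends on closure.

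**Early termination explains it.** The SAP text postdates the stop and deals with it for BSAI: "Due to the termination of the study data at later time points will be limited". It makes no comparable remark about closure, and readings before the stop remain usable.

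**The omission is disclosed.** Footnote e discloses one uncaptured visit. Table 1 still schedules ARANZ at Visits 1 to 17, so the footnote does not announce that the endpoint is gone.

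**The versions differ.** The SAP cites amendment 2, version 2, and the supplied protocol is version 3. That is a fair caveat on the comparison with the protocol. The conflict between SAP section 3 and SAP 8.6 is internal and survives it.

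**The counting rule matters only if closure is analysed.** Correct. It is content for the remedy and falls away if closure is openly dropped.

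**A larger effect might be inferred.** One could set newly closed wounds among those still assessed (20% at Month 12, simply the assumed q) against ever closed (59%) and present that as the ambiguity in protocol 14.3. The wording there does not support this: a patient whose wound closed earlier and is still closed has complete closure at the visit. The relevant contrast is the one in Step 4, and dropout handling (about 11 points) is at least as important as reopening (about 8) in the base case.

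**Intent.** A reader might also infer that closure was removed because of its results. Nothing in the documents shows a reason.

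**Conclusion.** The concern holds as an omission that should be fixed. The SAP retains the target-wound objective, plans no analysis of it, and does not say so in 5.2. That conclusion rests on the text alone. The sizes in Steps 2 to 6 rest on assumed rates and show only that a closure figure added without written rules could move by several to about 17 points on reasonable choices, and further if the general defaults were applied literally. SAP 6.3.1, the endpoint wording and the zero/above-zero split in 8.4 do point to patients with open wounds as the natural denominator, but no section ties them to a closure proportion.

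**What to change.** Add SAP 8.6.2 with one descriptive table, restricted to patients with baseline target wound area above zero, by prior SD-005 group and overall. No between-group comparison is needed, which fits SAP 7.1.

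- Report the proportion ever documented closed by each visit, retaining the first closure, with the number still under ARANZ follow-up at each visit.
- Do not count patients whose follow-up ended with the June 2018 stop as not closed at visits they never reached. Present cumulative closure censored at the last ARANZ reading, with the count over all initially unhealed patients alongside.
- State three limits: ARANZ does not capture reopening after closure; there is no Month 48/end-of-study wound reading; and censoring at early withdrawal may be informative, since protocol 8.4 names worsening lesions as a reason to consider discontinuation.

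In either case add an entry to SAP 5.2. It should say either that the by-visit proportion of protocol 14.3 is replaced by this measure, specified after early termination, or that closure is dropped, and why.

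The cost is SAP text and one table from readings already scheduled, or a sentence in 5.2; no new visits, patients or data. The drawbacks are that the rules are set after termination and that the table cannot show reopening.
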